6.10 Covariates

Stratified analyses specified in Section 7 will include adjustment for the stratification factors as recorded at randomization. Selected baseline values may be used as covariates in the exploratory analysis of efficacy endpoints.

6.11 Timing of Analyses

The SMC will periodically monitor the trial for safety during the treatment period. Three formal safety interim evaluations are planned:

- when approximately 12 patients (6 patients in 19A+RICE ARM) have been randomized and evaluated for DDTs delaying the Cycle 2 dose
- when the first 12 patients in the 19A+RICE Arm have been randomized and evaluated for DDTs delaying the Cycle 2 dose
- when the first 12 patients in the 19A+RICE Arm have completed cycle 3 or EOT

In addition, two interim administrative evaluations of the overall safety will be performed when approximately 40 and 75 patients have completed EOT. The hypothesis test that compares the CR rate of the 2 arms will not be performed. The study will not be discontinued unless there is a safety concern. A summary of activity may be used for risk/benefit assessment.

When conditions for these analyses are met, a cut-off date for the database will be determined and the analysis can take place. Data collected before this cut-off date will be analyzed. Every effort will be attempted to make the database as current and accurate as possible to the cut-off date.

The analysis of the primary endpoint of CR per IRF will occur after all patients have completed EOT response assessment. Comparison of the CR rates between the 2 treatment arms will be conducted. The database cutoff date for this analysis will be determined once all study patients have completed EOT.

The analysis of PFS and OS endpoints will occur approximately 2 years after the last patient's enrollment. If 70% of patients have experienced a PFS and/or OS event prior to 2 years after the last patient's enrollment, the analysis of PFS and/or OS may be performed earlier than scheduled. Subsequent cutoff dates may be defined and corresponding database locks may occur to allow for more precise estimates of the time-to-event endpoints prior to study closure.

7 PLANNED ANALYSES

7.1 Disposition

An accounting of study patients by disposition will be tabulated using the ITT and mITT analysis sets. The table will include the number and percentage of patients who were randomized, received study treatment, received treatment per randomization assignment, and participated in follow-up visits. The number and percentage of patients who discontinued treatment and study will be summarized. Number of patients who signed informed consent, the number of screen failures, and number of patients in each analysis set will be summarized for all randomized patients. Screen failures will also be described, if applicable.

The number and percentage of patients enrolled in each country and at each site will be summarized for all enrolled patients. Follow up time will be summarized.

Disposition data will be listed by patient using the ITT analysis set.

7.2 Demographic and Baseline Characteristics

Demographics and baseline characteristics, including age, gender, ethnicity, race, baseline height, weight, body mass index, and ECOG score will be listed and summarized using the ITT and mITT analysis set. Disease specific characteristics, including time from diagnosis and previous cancer-related treatments will be listed and summarized using the ITT and mITT analysis sets. Stratification factors at randomization will be summarized for ITT and mITT analysis set. Concordance of stratification factors used for randomization and recorded on baseline disease diagnosis CRF page will be presented.

7.3 Protocol Deviations

Important protocol deviations (defined as protocol violations by Seattle Genetics) are those that represent a divergence from the protocol that could have a significant effect on the integrity of the study data, or on the subject's rights, safety, or welfare. Important protocol deviations also include exemptions to the study inclusion/exclusion criteria and will be summarized by category. A list of patients with important protocol deviations will be presented.

7.4 Treatment Administration

Treatment administration will be summarized for each treatment component (denintuzumab mafodotin and each component of RICE) using the safety analysis set. Summary statistics for duration of therapy (in weeks) and the number of cycles per patient will be presented, as well as the number and percentage of patients who were treated at each cycle and completed each cycle. Cumulative dose, absolute dose intensity (ADI) and relative dose intensity (RDI) will be described. The number and percentage of patients whose dose was ever modified will be summarized by modification type, cycle and overall (i.e., over all drug administrations for a patient) for each treatment component. Listings may be presented as well. Dose modifications by dose may also be presented.

Duration of treatment (except when calculating exposure) is defined as the time from first dose date to the earliest of either:

1. last dose date + length of one dosing cycle, or
2. date of death

Intended Dose Intensity (IDI) is defined as the intended dose of drug (e.g., 3 mg/kg) per unit of time. The IDI for denintuzumab mafodotin and each component of RICE is presented in the following table.

Regimen Component	Intended Dose Regimen	Unit of time (weeks)	IDI
denintuzumab mafodotin	3 mg/kg	3	1
rituximab	375 mg/m ²	3	125.00
ifosfamide	5,000 mg/m ²	3	1666.67

carboplatin	AUC 5 mg/mL x min	3	1.67
etoposide	300 mg/m ²	3	100.00

Absolute Dose Intensity (ADI) is defined as the actual dose (e.g., mg/kg, mg/m² or AUC) per unit of time that the patient received over the entire treatment period. The treatment period will be the time from first dose date to (last dose date + length of one dosing cycle).

Relative Dose Intensity (RDI) is defined as the absolute dose intensity over the intended dose intensity where $RDI = ADI/IDI \times 100\%$.

Example 1

For denintuzumab mafodotin, consider a patient with an intended dose of 3 mg/kg, and is treated for three cycles (i.e., 9 weeks). For the last treatment the infusion was not completed and the patient received less than the full dose, as represented in the following table:

Visit	Intended Dose Regimen (mg/kg)	Weight (kg)	Intended Dose (mg)	Actual Dose (mg)	Duration (week)
C1D1	3	50	150	150	3
C2D1	3	52	156	156	3
C3D1	3	49	147	70	3

$$IDI = (3\text{mg/kg}) / (3 \text{ weeks}) = 1 \text{ mg/kg/week}$$

$$\begin{aligned} ADI &= (150\text{mg}/50\text{kg} + 156\text{mg}/52\text{kg} + 70\text{mg}/49\text{kg}) / (9 \text{ weeks}) \\ &= (3\text{mg/kg} + 3\text{mg/kg} + 1.43\text{mg/kg}) / (9 \text{ weeks}) \\ &= 0.82 \text{ mg/kg/week} \end{aligned}$$

$$\begin{aligned} RDI &= ADI/IDI \times 100\% = 0.826 / 1 \times 100\% \\ &= 82.6\% \end{aligned}$$

Example 2

For denintuzumab mafodotin, consider a patient with an intended dose of 3 mg/kg, and is treated for two cycles. Patient had one week delay before cycle 2, and died one week after the second dose.

Visit	Intended Dose Regimen (mg/kg)	Weight (kg)	Intended Dose (mg)	Actual Dose (mg)	Duration (week)
C1D1	3	50	150	150	3+1
C2D1	3	40	120	120	3*

*Although patient died one week after cycle 2 dosing, the duration is still 3 weeks for the purpose of calculating dose intensity.

$$IDI = (3\text{mg/kg}) / (3 \text{ weeks}) = 1 \text{ mg/kg/week}$$

$$ADI = (150\text{mg}/50\text{kg} + 120\text{mg}/40\text{kg}) / (4 + 3 \text{ weeks})$$

$$\begin{aligned}
 &= (3\text{mg/kg} + 3\text{mg/kg}) / (7 \text{ weeks}) \\
 &= 0.857 \text{ mg/kg/week} \\
 \text{RDI} &= \text{ADI/IDI} \times 100\% = 0.857 / 1 \times 100 \% \\
 &= 85.7\%
 \end{aligned}$$

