5.3.3 Dose and Administration

Patients in both treatment arms will receive RICE. In the 19A+RICE Arm, rituximab administration (as the first component of RICE) should be initiated approximately 30 to 60 minutes after the completion of denintuzumab mafodotin study drug infusion on Day 1.

Rituximab 375 mg/m² should be administered IV on Day 1 as the first component of RICE. The remaining RICE components may be administered in an order as per institutional standard of care. Typically, etoposide (100 mg/m² per day) is administered IV on Days 1 through 3; ifosfamide (5,000 mg/m²) is infused continuously in an inpatient setting for approximately 24 hours on Day 2 with mesna; and carboplatin (area under the curve 5 mg/mL x min; maximum dose, 800 mg) is administered IV on Day 2.

Dosing for RICE should be based on the patient's baseline (predose, Cycle 1 Day 1) height and weight or per institutional standards at the site.

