4 STUDY DESIGN

This is a randomized, open-label phase 2 study designed to compare the CR rates in patients with relapsed or refractory DLBCL who are candidates for ASCT. Approximately 100 patients will be randomized in a 1:1 ratio to 1 of 2 study arms:

- Control, RICE Arm: 3 cycles (3 weeks per cycle) of rituximab 375 mg/m² administered as the first component of RICE on Day 1 of every cycle; and followed by etoposide (100 mg/m² per day), ifosfamide (5,000 mg/m²) infused continuously with mesna, and carboplatin (area under the curve 5 mg/mL x min; maximum dose, 800 mg) administered during each cycle in an order as per institutional standard of care
- Investigational, 19A+RICE Arm: 3 cycles (3 weeks per cycle) of denintuzumab mafodotin 3 mg/kg on Day 1 of every cycle in conjunction with 3 cycles (3 weeks per cycle) of RICE; denintuzumab mafodotin is administered prior to the rituximab component of RICE therapy given on Day 1 of each cycle

A safety monitoring committee (SMC) comprising the study investigators, medical monitor, and study biostatistician will periodically monitor the safety of patients at predefined interim safety evaluations and during the treatment period. Upon its evaluation of the data, the SMC may recommend modification of the dose of denintuzumab mafodotin in the 19A+RICE Arm (e.g., to 2 mg/kg) in subsequently enrolled patients. If dose modification is necessary, up to 50 additional patients may be randomized (25 in each arm) so that a total of 100 patients will be randomized in a 1:1 ratio to receive either 19A (modified dose) + RICE or RICE alone.

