6.4 Data Transformations and Derivations

Reported age in years will be used; if not available, age in years will be calculated with the SAS INTCK function (with method specified as “continuous”) using date of randomization and birth date.

Study Day will be calculated as Date–First Dose Date+1 for dates on or after the first dose date unless otherwise specified. For dates prior to the first dose date, Study Day will be calculated as Date–First Dose Date. For all calculations of Study Day, the First Dose Date will be the earliest date of treatment administration for denintuzumab mafodotin or RICE.

Other time variables based on two dates, e.g., Start Date and End Date, will be calculated as (End Date–Start Date+1) (in days) unless otherwise specified in the planned analysis section.

The following unit conversion will be implemented unless otherwise specified:

$$\text{Months} = \text{Days} / 30.4375$$

$$\text{Years} = \text{Days} / 365.25$$

Unless otherwise specified, baseline values used in all analyses will be the most recent non-missing measurement prior to the first dose of study treatment.

The end-of-treatment (EOT) date will be the date the EOT visit is performed; if an EOT visit is not performed then the EOT date will be either the EOS date or 30 days after the last dose of any study treatment, whichever is earlier.

For efficacy assessments by investigator, the date of response assessment (CR, PR or SD) will be the latest of all radiologic scan dates for the given restage assessment. The date of progression will be the earliest of all radiologic scan dates for the given restage assessment, or the date of investigator claim of clinical progression. Patients who have a response of Stable Disease or better per Lugano criteria at the same visit as investigator claim of clinical progression will be counted as clinical progression. At EOT, an adequate tumor assessment must include a radiologic scan that is evaluable for response per Lugano classification criteria. However, an investigator claim of clinical progression is adequate for an assessment of disease progression. During long-term follow-up, for those patients who achieved a response, a physical exam is adequate for determining a patient has not progressed by investigator assessment.

For efficacy assessments by IRF, the date of progression and response will be specified in the IRF charter.

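### The SAP's dose-intensity period does not fit etoposide: a patient given every dose in full and on schedule scores 96.9% after three cycles, not 100%

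*SAP*

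**What the plan says.** SAP 7.4 applies one method to all drugs: "Treatment administration will be summarized for each treatment component (denintuzumab mafodotin and each component of RICE) using the safety analysis set". "Intended Dose Intensity (IDI) is defined as the intended dose of drug (e.g., 3 mg/kg) per unit of time", and the accompanying table sets etoposide at 300 mg/m² over 3 weeks, or 100 per week. Absolute dose intensity (ADI) is the dose received divided by the length of the treatment period: "The treatment period will be the time from first dose date to (last dose date + length of one dosing cycle"). RDI is ADI divided by intended dose intensity (IDI), times 100%.

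Protocol 5.3.3 describes the usual schedule: "etoposide (100 mg/m² per day) is administered IV on Days 1 through 3". The sentence is introduced as typical practice, not as a requirement. Note Y to the schedule of events (Protocol Appendix A) also places RICE on Days 1–3, within a day either way, in both arms.

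For carboplatin, the IDI table lists "AUC 5 mg/mL x min" per 3 weeks (1.67 per week). The regimen in SAP 4 is "area under the curve 5 mg/mL x min; maximum dose, 800 mg". SAP 7.4 allows the actual dose to be expressed in AUC but does not say how a capped dose is converted.

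**The concern.** The numerator and the IDI count whole cycles of exactly 3 weeks, whereas the denominator counts calendar time from the first dose to one cycle after the last dose. The two agree only when a drug's first and last doses fall on the same day of the cycle. That holds for denintuzumab mafodotin and rituximab (Day 1). It does not hold for etoposide, whose first dose is on Day 1 and whose last dose is on Day 3. A table produced from the literal rule would show etoposide under-delivery in patients who missed nothing. The shortfall is largest in patients who stop early, because the 2 extra days are spread over fewer cycles.

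The carboplatin entry raises a related question: whether a patient dosed at the regimen's own maximum is measured against a target that the regimen does not allow.

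**Working it through.** **Reproducing the SAP's examples.** Count Cycle 1 Day 1 as day 1.

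- Example 1 (three on-time doses on days 1, 22 and 43): period = 43 + 21 − 1 = 63 days = 9 weeks. ADI = (3 + 3 + 1.43)/9 = 0.826 and RDI = 82.6%, as printed.
- Example 2 (one-week delay, doses on days 1 and 29): period = 29 + 21 − 1 = 49 days = 7 weeks. ADI = 6/7 = 0.857 and RDI = 85.7%, as printed.

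Both match the rule without an added day.

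**Etoposide, all doses full and on schedule.** Inputs: 300 mg/m² per cycle and IDI 100 per week (SAP 7.4), 21-day cycles with a maximum of three (Protocol synopsis), Days 1–3 (Protocol 5.3.3). For n cycles the last dose falls on day 21(n − 1) + 3, so the period is 21(n − 1) + 3 + 21 − 1 = 21n + 2 days. RDI = [300n ÷ ((21n + 2)/7)] ÷ 100 = 21n/(21n + 2).

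| Cycles | Last dose (day) | Period (days) | RDI by the rule | RDI on cycle time (21n days) |
|---|---|---|---|---|
| 3 | 45 | 65 | 63/65 = 96.9% | 100% |
| 2 | 24 | 44 | 42/44 = 95.5% | 100% |
| 1 | 3 | 23 | 21/23 = 91.3% | 100% |

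**Other components.** With first and last dose dates taken per component, rituximab (Day 1) and ifosfamide and uncapped carboplatin (typically Day 2) all score 100%: their periods are exactly 21n days.

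**Why both ends of the period need an anchor.** Suppose only the end were moved to Day 1 of the last cycle, with the start left at the component's first dose. A Day 2 drug would then have a period of 21n − 1 days and would score 63/62 = 101.6%, 42/41 = 102.4% or 21/20 = 105.0% after 3, 2 or 1 cycles. If the first dose date were instead the study-level date that SAP 6.4 defines for Study Day, the current rule would already give Day 2 drugs 63/64 = 98.4% over three cycles. Anchoring both ends to cycle Day 1 gives 21n days for every drug on schedule under either reading.

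**Carboplatin at the cap (conditional).** If delivered AUC is used as actual dose, a capped patient receives 5 × 800/D, where D is the calculated AUC 5 dose in mg, and RDI = 800/D. The documents give no distribution of D. For assumed values of 850, 900 and 1000 mg, RDI is 94.1%, 88.9% and 80.0%. At or below 800 mg there is no effect.

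**The case against.** The strongest reply is that the worked examples show the intent. Each has a per-cycle duration column that is summed (3 + 3 + 3, and 4 + 3 weeks). Applied to etoposide, that gives 9 weeks and 100%. This is a fair reading, and it supports calling the problem a gap in wording. It does not remove the gap: both examples concern a Day 1 drug, for which summing cycles and counting dates coincide, and the only rule stated in words is the date rule.

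A reader might infer several stronger points that the documents do not support.

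- **That etoposide can never reach 100%.** The Days 1–3 schedule is typical, not mandatory, and Cycles 2 and 3 may start a day early or late. If each starts one day early relative to the previous cycle, the last dose falls on day 43, the period is 63 days and the score is 100%.
- **That every drug is understated because of the added-day default.** Under SAP 6.4, time variables based on two dates "will be calculated as (End Date–Start Date+1) (in days) unless otherwise specified in the planned analysis section". The 9- and 7-week examples in SAP 7.4 do specify otherwise.
- **That the comparison of arms is biased.** Both arms receive the same RICE, so the offset largely cancels. As an assumed illustration, if 80/10/10% of one arm and 60/20/20% of the other receive 3/2/1 cycles, mean etoposide RDI is 96.2% against 95.5%, a gap of 0.7 points.
- **That RDI is the plan's key evidence on backbone delivery.** The SAP says only that it will be described, alongside cycles received, cumulative dose and dose modifications. No test or threshold depends on it.
- **That every capped carboplatin patient is scored as under-dosed.** This follows only if the capped dose is converted back to delivered AUC. If it is recorded as AUC 5, nothing is lost, and comparing delivered with target AUC is itself a defensible definition once stated.

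**Conclusion.** The concern holds for etoposide and is minor. On the literal rule and the typical Days 1–3 schedule, full on-time dosing is understated by 3.1, 4.5 or 8.7 percentage points after 3, 2 or 1 cycles. The largest figure applies only to patients who stop after one cycle. The carboplatin point is secondary: it depends on how actual AUC is derived and on how many patients have a calculated dose above 800 mg, which the documents do not show. Only descriptive exposure tables are affected; no hypothesis test, efficacy estimate or sample size changes.

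**What to change.** In SAP 7.4:

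1. Define the dose-intensity period for every component as Day 1 of the first cycle in which the component was given to Day 1 of the last such cycle plus 21 days, and state that the added-day default of SAP 6.4 does not apply. This reproduces the 63- and 49-day denominators of Examples 1 and 2, still counts delays between cycles, and gives 100% for full on-time dosing of etoposide and of the Day 2 drugs.
2. For carboplatin, and for RDI only, take the intended dose as the smaller of the calculated AUC 5 dose and the protocol's existing 800 mg maximum, and state the unit in which actual dose is derived.
3. Add a short worked example for etoposide.

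The cost is SAP wording and a change to one derivation. The period change needs only cycle and dosing dates; the carboplatin change also needs the calculated AUC 5 dose for capped patients, so confirm that it is recorded or can be derived. Nothing about dosing changes.

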7.5 Efficacy Analyses

The primary analysis CR rate will be based on the mITT analysis set. Secondary efficacy endpoint of response rate will also be summarized using the mITT analysis set. Secondary efficacy analysis of time to event endpoints will be summarized using the mITT analysis set. Additional analyses of efficacy endpoints using the ITT, safety, and per-protocol analysis sets will also be presented as appropriate. Analyses may also be performed using the subgroups listed in Section 6.8. For efficacy analyses, study day will be counted from date of randomization, i.e. Study Day = Date – Randomization Date + 1.

7.5.1 Primary Endpoint

7.5.1.1 Complete Remission (CR) Rate

The primary analysis for CR rate will be performed for mITT Analysis Set based on IRF assessment. CR rate is defined as the proportion of patients achieving CR (CMR by PET or CR by PET) at the EOT assessment using the Lugano classification criteria (Cheson 2014). The hypotheses will be tested at a two-sided 0.1 alpha level using a Cochran-Mantel-Haenszel (CMH) test stratified by the randomization strata (see Section 6.3). In situations where a stratum cannot be included in a stratified analysis of an endpoint, it may be necessary to pool strata prior to the analysis (Section 6.6).

The null and alternative hypotheses can be written respectively as:

H_0 : The two treatments have equal CR rates with respect to the common odds ratio ($OR=1$).

H_A : The two treatments have different CR rates with respect to the common odds ratio ($OR \neq 1$).

The CR rate and exact two-sided 90% CI using the Clopper-Pearson method (Clopper 1934) will be presented by stratification factor and overall.

The Mantel-Haenszel estimate of the common CR rate difference adjusted for the randomization strata and 90% stratified Newcombe confidence interval (Yan and Su 2010) may be presented.

Secondary Analyses

The secondary analyses will be performed the same way as the CR rate per IRF. The secondary analysis of CR rate will be performed for CR rate per investigator based on the mITT Analysis Set.

Sensitivity Analyses

Sensitivity analyses of CR rate will be performed if appropriate. Sensitivity analyses may include, but will not be limited to, the following

1. Analyses for CR rate at EOT for ITT, Safety and PP analysis sets
2. CMH test stratified by stratification factors recorded on baseline disease diagnosis CRF page for CR rate
3. An unstratified test for CR rate

The concordance in response assessment between IRF and investigator assessment will be summarized. The Kappa statistic may be calculated to evaluate the agreement between IRF and investigator assessment.

The determination of antitumor activity will be based on response assessments made according to the Lugano Classification criteria (Cheson 2014). Staging will be performed by PET/CT of diagnostic quality, with disease involvement determined by focal FDG uptake in nodal and extranodal (including spleen, liver, bone marrow, and thyroid) sites that is consistent with lymphoma, according to the pattern of uptake and/or CT characteristics. Lugano 5 Point Score by IRF and by investigator assessment will be summarized by response as appropriate. The concordance of the Lugano 5 Point Score between the IRF and the investigator assessment will be summarized as appropriate.

SPD for target lesions is defined as the sum of the products of diameters of the target lesions. The SPD change from baseline will be derived for each patient. The maximum SPD percent reduction (or minimum percent increase if there is no reduction) for each patient will be graphically displayed (e.g., using a waterfall plot).

The Minimal Residual Disease (MRD) status will be explored. The CR achieved after EOT assessment may also be explored.

